		
 • EQ-5D-5L UK population-based index score (health state index) 	Derive EQ-5D-5L UK Population-based index score according to the link by using the UK algorithm to produce a patient-level index score between -0.59 and 1.0 (continuous variable).	N/A – partial assessments cannot be saved on the eCOA tablet.
		
 • Change from baseline in EQ-5D-5L UK population-based index score 	Change from baseline: observed EQ-5D-5L UK score – baseline EQ-5D-5L UK score	Missing if baseline or observed value is missing.
		
 • EQ-5D-5L US population-based index score (health state index) 	Derive EQ-5D-5L US Population-based index score according to the link by using the US algorithm to produce a patient-level index score between -0.11 and 1.0 (continuous variable).	N/A – partial assessments cannot be saved on the eCOA tablet.

Measure	Description	Variable	Derivation / Comment	Imputation Approach if Missing Components
	weights) to each of the levels in each dimension (Herdman et al. 2011; EuroQol Group 2015 [WWW]).	
 Change from baseline in EQ-5D-5L US population-based index score 	Change from baseline: observed EQ-5D-5L US score – baseline EQ-5D-5L US score	Missing if baseline or observed value is missing.

Abbreviations: AD = atopic dermatitis; eCOA = electronic clinical outcomes assessment; N/A = not applicable, QoL = quality of life; UK = United Kingdom; US = United States.

Table JAHN.6.7. Description of Health Outcomes and Quality-of-Life Measures Analyses

Measure	Variable	Population ^a (Section 6.2.1)	Analysis Method ^b (Section 6.2.3)	Time Point	Analysis Type
Itch Numeric Rating Scale (NRS)	Itch NRS score Change from baseline in Itch NRS score Percent change from baseline in Itch NRS score	mITT population entering the downtitration and withdrawal study (Period 2) mITT population entering the downtitration and withdrawal study (Period 2) with Week 52 IGA of 0 or 1	ANCOVA using mLOCF	Weeks 52-68	Exploratory analysis
	Proportion of patients with a 4-point improvement from baseline of originating study in Itch NRS in subgroup of patients who had baseline Itch NRS ≥ 4	mITT population entering the downtitration and withdrawal study (Period 2) mITT population entering the downtitration and withdrawal study (Period 2) with Week 52 IGA of 0 or 1	Logistic regression using NRI and mLOCF	Weeks 52-68	Exploratory analysis
Skin Pain NRS	Skin Pain NRS score Change from baseline in Skin Pain NRS score	mITT population entering the downtitration and withdrawal study (Period 2) mITT population entering the downtitration and withdrawal study (Period 2) with Week 52 IGA of 0 or 1	ANCOVA using mLOCF	Weeks 52-68	Exploratory analysis
Skin Pain NRS	Proportion of patients with a 4-point improvement from baseline of originating study in Skin Pain in subgroup of patients who had baseline Skin Pain NRS ≥ 4	mITT population entering the downtitration and withdrawal study (Period 2) mITT population entering the downtitration and withdrawal study (Period 2) with Week 52 IGA of 0 or 1	Logistic regression using NRI and mLOCF	Weeks 52-68	Exploratory analysis

Measure	Variable	Population ^a (Section 6.2.1)	Analysis Method ^b (Section 6.2.3)	Time Point	Analysis Type
Atopic Dermatitis Sleep Scale (ADSS)	ADSS item scores Change from baseline in ADSS item scores	mITT population entering the downtitration and withdrawal study (Period 2) mITT population entering the downtitration and withdrawal study (Period 2) with Week 52 IGA of 0 or 1	ANCOVA using mLOCF	Weeks 52-68	Exploratory analysis
	Proportion of patients with a 2-point improvement from baseline of originating study in item 2 score of ADSS, in a subgroup of patients with baseline item 2 score of ≥ 2 Proportion of patients with a 1.5-point improvement from baseline of originating study in Item 2 score of ADSS, in a subgroup of patients with baseline item 2 score of ≥ 1.5	mITT population entering the downtitration and withdrawal study (Period 2) mITT population entering the downtitration and withdrawal study (Period 2) with Week 52 IGA of 0 or 1	Logistic regression using NRI and mLOCF	Weeks 52-68	Exploratory analysis
Patient Global Impression of Severity–Atopic Dermatitis (PGI-S-AD)	PGI-S-AD score Change from baseline in PGI-S-AD score	mITT population entering the downtitration and withdrawal study (Period 2) mITT population entering the downtitration and withdrawal study (Period 2) with Week 52 IGA of 0 or 1	ANCOVA using mLOCF	Weeks 52-68	Exploratory analysis
Patient-Oriented Eczema Measure (POEM) ^c	POEM score Change from baseline in POEM score	mITT population from originating combination therapy study -responders, partial responders	Descriptive using observed and mLOCF	Weeks 0-52	Exploratory analysis

Measure	Variable	Population ^a (Section 6.2.1)	Analysis Method ^b (Section 6.2.3)	Time Point	Analysis Type
		mITT population from originating combination therapy study -non responders	MMRM using observed Descriptive using mLOCF	Weeks 0-52	Exploratory analysis
		mITT population from open-label study	Descriptive using observed and mLOCF	Weeks 0-52	Exploratory analysis
		Randomized Downtitration Withdrawal Substudy Population	ANCOVA using mLOCF	Weeks 52-200	Exploratory analysis
		Randomized Downtitration Withdrawal Substudy Population with Week 52 IGA of 0 or 1			
		Period 2 non-substudy population Open-label Period 2 non-substudy population	Descriptive using observed and mLOCF	Week 52 to 200	Exploratory
	Proportion of patients with a 4-point improvement in POEM score from baseline of originating study in a subgroup of patients with baseline POEM ≥ 4	mITT population from originating combination therapy study - responders, partial responders	Descriptive using observed and mLOCF	Weeks 0-52	Exploratory analysis
		mITT population from originating combination therapy study - nonresponders	Logistic regression using NRI Descriptive using mLOCF	Weeks 0-52	Exploratory analysis
		mITT population from open-label study	Descriptive using observed and mLOCF	Weeks 0-52	Exploratory analysis

Measure	Variable	Population ^a (Section 6.2.1)	Analysis Method ^b (Section 6.2.3)	Time Point	Analysis Type
Patient-Oriented Eczema Measure (POEM) ^c	Proportion of patients with a 4-point improvement in POEM score from baseline of originating study in a subgroup of patients with baseline POEM ≥ 4	All patients Randomized Downtitration Withdrawal Substudy Population Randomized Downtitration Withdrawal Substudy Population with Week 52 IGA of 0 or 1	Logistic regression using NRI and mLOCF	Weeks 52-200	Exploratory analysis
		Period 2 non-substudy population Open-label Period 2 non-substudy population	Descriptive using Observed, mLOCF and NRI	Week 52 to 200	Exploratory Primary for mLOCF Sensitivity for NRI
Hospital Anxiety Depression Scale (HADS)	Observed and change from baseline in HADS domain scores Change from baseline in HADS total score	mITT population from originating combination therapy study - responders, partial responders	Descriptive using observed and mLOCF	Weeks 0-52	Exploratory analysis
		mITT population from originating combination therapy study - nonresponders	MMRM using observed Descriptive using mLOCF	Weeks 0-52	Exploratory analysis
		mITT population from open-label study	Descriptive using observed and mLOCF	Weeks 0-52	Exploratory analysis
		Period 2 non-substudy population Open-label Period 2 non-substudy population	Descriptive using observed and mLOCF	Week 52 to 104	Exploratory
Dermatology Life Quality Index (DLQI) ^c	DLQI total score Observed and change from baseline in domain scores	mITT population from originating combination therapy study - responders, partial responders	Descriptive using observed and mLOCF	Weeks 0-52	Exploratory analysis

Measure	Variable	Population ^a (Section 6.2.1)	Analysis Method ^b (Section 6.2.3)	Time Point	Analysis Type
		mITT population from originating combination therapy study - nonresponders	MMRM using observed Descriptive using mLOCF	Weeks 0-52	Exploratory analysis
		mITT population from open-label study	Descriptive using observed and mLOCF	Weeks 0-52	Exploratory analysis
		Randomized Downtitration Withdrawal Substudy Population	ANCOVA using mLOCF	Weeks 52-200	Exploratory analysis
		Randomized Downtitration Withdrawal Substudy Population with Week 52 IGA of 0 or 1			
		Period 2 non-substudy population Open-label Period 2 non-substudy population	Descriptive using observed and mLOCF	Week 52 to 200	Exploratory
		Long term Baricitinib 4 mg population	Descriptive using observed and mLOCF	Weeks 52-200	Exploratory
	Proportion of patients with DLQI (0,1) Proportion of patients with a 4-point improvement from baseline in originating study in a subgroup of patients with baseline DLQI score ≥ 4	mITT population from originating combination therapy study - responders, partial responders	Descriptive using observed and mLOCF	Weeks 0-52	Exploratory analysis

Measure	Variable	Population ^a (Section 6.2.1)	Analysis Method ^b (Section 6.2.3)	Time Point	Analysis Type
		mITT population from originating combination therapy study - nonresponders	Logistic regression using NRI Descriptive using mLOCF	Weeks 0-52	Exploratory analysis
		mITT population from open-label study	Descriptive using observed and mLOCF	Weeks 0-52	Exploratory analysis
Dermatology Life Quality Index (DLQI) ^c	Proportion of patients with DLQI (0,1) Proportion of patients with a 4-point improvement from baseline in originating study in a subgroup of patients with baseline DLQI score ≥ 4	Randomized Downtitration Withdrawal Substudy Population	Logistic regression using NRI and mLOCF	Weeks 52-200	Exploratory analysis
		Randomized Downtitration Withdrawal Substudy Population with Week 52 IGA of 0 or 1			
		Period 2 non-substudy population Open-label Period 2 non-substudy population	Descriptive using mLOCF and NRI	Week 52 to 200	Exploratory Primary for mLOCF Sensitivity for NRI
		Long term Baricitinib 4 mg population	Descriptive using observed, NRI and mLOCF	Weeks 52-200	Exploratory
Work Productivity and Activity Impairment: Atopic Dermatitis (WPAI-AD)	Observed and change from baseline in employment status: 
 ▪ absenteeism ▪ presenteeism ▪ overall work impairment impairment in activities	mITT population from originating combination therapy study - responders, partial responders	Descriptive using observed and mLOCF	Weeks 0-52	Exploratory analysis
		mITT population from originating combination therapy study - nonresponders	MMRM using observed Descriptive using mLOCF	Weeks 0-52	Exploratory analysis

Measure	Variable	Population ^a (Section 6.2.1)	Analysis Method ^b (Section 6.2.3)	Time Point	Analysis Type
		mITT population from open-label study	Descriptive using observed and mLOCF	Weeks 0-52	Exploratory analysis
European Quality of Life-5 Dimensions-5 Levels (EQ-5D-5L)	Observed and change from baseline in: 
 ▪ EQ-5D mobility ▪ EQ-5D self-care ▪ EQ-5D usual activities ▪ EQ-5D pain/discomfort EQ-5D anxiety/depression	mITT population from originating combination therapy study - responders, partial responders	Descriptive using observed and mLOCF	Weeks 0-52	Exploratory analysis
		mITT population from originating combination therapy study - nonresponders	MMRM using observed Descriptive using mLOCF	Weeks 0-52	Exploratory analysis
		mITT population from open-label study	Descriptive using observed and mLOCF	Weeks 0-52	Exploratory analysis

Abbreviations: ANCOVA = analysis of covariance; EE = efficacy evaluable; IGA = Investigator’s Global Assessment; mITT = modified intent-to-treat; mLOCF = modified last observation carried forward; MMRM = mixed-model repeated measures; NRI = nonresponder imputation; VAS = visual analog scale.

- ^a Populations from originating studies for reporting periods of Week 0-52 are on the mITT population; they are reported by responder status from originating study: responders, partial responders, responders + partial responders, and nonresponders.
- ^b All categorical endpoints use NRI, unless otherwise stated.
- ^c Descriptive using observed data for the endpoints beyond Week 104, unless otherwise stated.

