For patients who do not require washout, baseline will be the last visit of the originating study. Patients who received oral systemic AD treatment as rescue therapy during the originating study require a 4-week washout and will have an additional screening visit in Study JAHN (Visit 1 [Week 0]). The assessments collected at this visit will provide the Study JAHN baseline for these patients. If labs were not collected at this visit, then the most recent lab value collected at the last visit of the originating study will be used as baseline.

Period 2

For analysis of endpoints assessed at scheduled visits in Period 2, baseline from originating study will be used for categorical endpoints, such as EASI75, Itch NRS ≥ 4 -point improvement response, etc. Baseline from originating study will also be used for EASI-related, continuous endpoints, such as EASI change or percent change from baseline. For the other continuous endpoints such as Itch NRS and DLQI change from baseline, the analysis will be done using the Week 52 baseline. The methodology for defining Week 52 as the baseline is the same as the methodology for defining Week 0 of the originating study described above, anchoring on the first study drug administration of Period 2.

Safety Analyses

Safety analyses for treatment Period 1, and for Treatment Periods 1 and 2 combined (box plots of laboratory analytes and vital signs) will be conducted using the Study JAHN baseline, which is defined as the last nonmissing scheduled (planned) measurement on or prior to the date of first study drug administration for continuous measures by-visit analyses and non-missing measurements on or prior to the date of first study drug administration in Study JAHN for all other analyses. Safety analyses for Treatment Period 2 will be conducted for AEs only. Baseline for Treatment Period 2 is defined as nonmissing measurements on or prior to the date of first study drug administration in Treatment Period 2 of Study JAHN.

Postbaseline

Period 1(Weeks 0 to 52)

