 - If year of onset is missing, duration of AD will be set as missing. Otherwise, unknown month will be taken as January, and unknown day will be taken as 01. The duration of AD will be rounded to 1 decimal place.
- duration of AD (years) category (0 to <2 years, 2 to <5 years, 5 to <10 years, 10 to <20 years, ≥20 years)
- diagnosis age (year), derived using diagnosis date as the reference start date and July 1st of birth year and truncated to a whole-integer age
- diagnosis age group (<18, ≥18 to <50, ≥50 years old)
- change from baseline = postbaseline measurement at Visit x – baseline measurement from originating study
 - If a baseline value is missing, it will not be imputed and the change from baseline will not be calculated.
- percent change from baseline at Visit x:

$$([\text{postbaseline measurement at Visit x} - \text{baseline measurement}] / \text{baseline measurement}) * 100$$
 - If a baseline value is missing, it will not be imputed and percent change from baseline will not be calculated.
- Weight (kg) = weight (lbs) * 0.454
- Weight category (<60 kg, ≥60 to <100 kg, ≥100 kg)
- Height (cm) = height (in) * 2.54
- cyclosporine inadequate efficacy prior to entry into originating study (yes, no)
 - Set to **yes** if the reason for discontinuation is inadequate response.

- cyclosporine intolerance prior to entry into originating study (yes, no)
 - Set to **yes** if the reasons for discontinuation are: intolerance to medication or contraindication (physician indicated cyclosporine was used and a contraindication was noted).
- cyclosporine contraindication (ineligible) prior to entry into originating study (yes, no)
 - Set to **yes** if cyclosporine was never used because of a contraindication.
- cyclosporine inadvisable prior to entry into originating study (yes, no)
 - Set to **yes** if the following reasons were selected for either not using the medication or discontinuing the medication:
 - reason for not using medication: physician decision, concern about side effects, unfavorable benefit risk, contraindication.
 - reasons for discontinuation: inadequate response, intolerance to medication, or contraindication.
- TCNI inadequate efficacy prior to entry into originating study (yes, no)
 - Set to **yes** if the reason for discontinuation is inadequate response.
- TCNI intolerance prior to entry into originating study (yes, no)

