SCORing Atopic Dermatitis	Change from baseline in SCORAD score	mITT population from open-label study	Descriptive using observed and mLOCF	Weeks 0-52	Exploratory

Measure	Variable	Population ^a (Section 6.2.1)	Analysis Method ^b (Section 6.2.3)	Time Point	Analysis Type
(SCORAD) ^c	Percent change from baseline in SCORAD score	Period 2 non-substudy population Open-label Period 2 non-substudy population	Descriptive using observed and mLOCF	Weeks 52-200	Exploratory
	SCORAD score, Pruritus & Sleep Loss Percent change from baseline in SCORAD score, Pruritus & Sleep Loss	Long term Baricitinib 4 mg population	Descriptive using observed and mLOCF	Weeks 52-200	Exploratory
	Proportion of patients achieving SCORAD75 Proportion of patients achieving SCORAD90	mITT population from originating combination therapy study - responders, partial responders	Descriptive using NRI and mLOCF	Weeks 0-52	Exploratory
		mITT population from originating combination therapy study - nonresponders	Logistic regression using NRI Descriptive using mLOCF	Weeks 0-52	Exploratory
		mITT population from open-label study	Descriptive using NRI and mLOCF	Weeks 0-52	Exploratory
		Period 2 non-substudy population Open-label Period 2 non-substudy population	Descriptive using observed, NRI and mLOCF	Weeks 52-200	Exploratory
		Long term Baricitinib 4 mg population	Descriptive using NRI, observed and mLOCF	Weeks 52-200	Exploratory

Abbreviations: AD = atopic dermatitis; ANCOVA = analysis of covariance; Bari = baricitinib; DBL = database lock; EE = efficacy evaluable; Feb = February; mITT = modified intent-to-treat; mLOCF = modified last observation carried forward; MMRM = mixed-model repeated measures; NRI = nonresponder imputation.

- ^a Populations from originating studies for reporting periods of Weeks 0-52 are on the mITT population; they are reported by responder status from originating study: responders, partial responders, responders + partial responders and nonresponders. Populations for visit-wise analyses for those who entered the randomized withdrawal and downtitration study are based on efficacy evaluable sets for each of Week 56, 60, 64, and 68 (defined in Section 6.2.1).
- ^b All categorical endpoints use NRI, unless otherwise stated.
- ^c Descriptive using observed data for the endpoints beyond Week 104, unless otherwise stated.

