6.11.3. Sensitivity Analyses

Sensitivity analyses are included to demonstrate robustness of analyses methods using different censoring rules, populations, and analyses assumptions. Sensitivity analyses for select outcomes have been previously described and include the following:

- analysis of select continuous outcomes with ANCOVA (Section 6.2.3), with missing data imputed using mLOCF (Section 6.4.3)
- analysis of select continuous outcomes in the randomized withdrawal and downtitration substudy using Week 52 as the baseline
- analysis of selected outcomes (IGA, EASI, ITCH-NRS), with missing data imputed using mLOCF

For analyses on and after the February 2021 DBL, NRI will be used as supportive sensitivity.

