- EASI change and percent change from baseline assessed at Weeks 0 to 48 based on observed data.

- Summary of sponsor provided TCS background therapy weight (g) by potency for weeks 0 to 52.

For the substudy the following analyses/summaries will be provided:

- Proportion of patients achieving IGA (0,1) and IGA (0,1,2) assessed at Weeks 52 to 68.
- Proportion of patients achieving EASI50, EASI75, and EASI90 assessed at Weeks 52 to 68.
- EASI change from baseline and percent change from baseline (mLOCF) assessed at Weeks 52 to 68; Week 0 used as baseline.
- EASI change from baseline and percent change from baseline (mLOCF) assessed at Weeks 52 to 68; Week 52 used as baseline.
- Proportions of patients achieving a ≥ 4 -point improvement assessed at Weeks 52 to 68.
- Itch NRS change from baseline and percent change from baseline (mLOCF) assessed at Weeks 52 to 68; Week 0 used as baseline.
- Itch NRS change from baseline and percent change from baseline (mLOCF) assessed at Weeks 52 to 68; Week 52 used as baseline.

Signature Page for VV-CLIN-127789 v1.0

Approval	PPD 25-Aug-2023 13:26:21 GMT+0000
----------	--------------------------------------

Signature Page for VV-CLIN-127789 v1.0

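### In the Period 2 substudy, percent change in itch is divided by the Week 52 score, which can be zero or close to it, and the SAP has no rule for that case

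*SAP*

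**What the plan says.** SAP Table JAHN.6.7 (Section 6.12) puts three itch variables in one Period 2 row: the score, the change and "Percent change from baseline in Itch NRS score". The method is "ANCOVA using mLOCF", the time point is Weeks 52-68 and the status is exploratory. The row covers everyone entering the substudy and, separately, those with Week 52 IGA 0 or 1.

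Section 6.2.2 sets the Period 2 baseline by endpoint. For EASI: "Baseline from originating study will also be used for EASI-related, continuous endpoints, such as EASI change or percent change from baseline". For the rest: "For the other continuous endpoints such as Itch NRS and DLQI change from baseline, the analysis will be done using the Week 52 baseline". Section 6.2.3 makes ANCOVA the primary method for continuous Period 2 variables, adjusted for region, Week 52 severity and Week 52 value.

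Section 6.2.4 defines percent change as (postbaseline - baseline) / baseline x 100. Its only provision for an unusable denominator is: "If a baseline value is missing, it will not be imputed and percent change from baseline will not be calculated". Table JAHN.6.6 likewise sets percent change in itch to missing only when a value is missing, although 0 is a valid score meaning no itch.

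Two other places bear on this. Appendix 2, for the May 2020 safety-update lock, lists "Itch NRS change from baseline and percent change from baseline (mLOCF) assessed at Weeks 52 to 68; Week 52 used as baseline" beside a Week 0 version. Section 6.11.3 plans an "analysis of select continuous outcomes in the randomized withdrawal and downtitration substudy using Week 52 as the baseline" without naming the outcomes.

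**The concern.** Percent change works when everyone starts well away from zero, as at entry to an originating study. The substudy admits only patients with IGA 0, 1 or 2 at Week 52, after a year or more in the programme, so some may have little or no itch. Two things then follow from the formula.

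- A patient with a Week 52 weekly mean of 0 has no percent change. By default the patient is lost from a randomised comparison because of a complete itch response, and the analysed set is no longer the population named in the table.
- A patient with a small non-zero mean can contribute a value in the thousands of percent on relapse. That variable goes into a linear model of means that assumes roughly even scatter.

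At stake is whether the least-squares mean difference and p-value for itch percent change say anything useful about withdrawal or down-titration.

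**Working it through.** The plan states no power or precision figure for this endpoint, so there is none to reproduce. The check has two parts.

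**1. The formula at different denominators**

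Inputs: Itch NRS runs from 0 to 10 (Table JAHN.6.6). The diary baseline is a mean over 7 days with at least 4 values (Section 6.2.2), so the smallest non-zero full-week mean is 1/7.

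- Baseline 0: division by zero, no value.
- From 1/7 to 5: (5 - 1/7) / (1/7) x 100 = (35 - 1) x 100 = +3400%.
- Ceiling from 1/7: (10 - 1/7) / (1/7) x 100 = (70 - 1) x 100 = +6900%. The floor is always -100%.
- The same 2-point rise: 2 / (1/7) = +1400%; 2 / 0.5 = +400%; 2 / 2 = +100%; 2 / 7 = +29%.

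For comparison, EASI percent change from the originating baseline cannot meet this problem. Entry requires EASI of at least 16 (Protocol Addendum Section 4.5.1, stated there to match the feeder studies), so the largest possible value is (72 - 16) / 16 x 100 = +350%.

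**2. Effect on the ANCOVA, by simulation**

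Arm size: about 600 substudy patients (SAP Section 6.1), two entry doses and 1:1:1 rerandomisation (Section 5.2) give 600 / 2 / 3 = 100 per arm, if the doses split equally. Everything else is assumed, because the documents give no Week 52 itch distribution: gamma-distributed Week 52 itch, a share of added exact zeros, and a true arm difference of 1 point. The ANCOVA was on arm and Week 52 value, with zero baselines treated as missing for percent change.

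| Assumed Week 52 mean | Added zeros | Residual SD | Power, % change from Week 52 | Power, absolute change |
|---|---|---|---|---|
| 1.5 | 0-20% | 2.0 | 45-54% | 92-93% |
| 2.5 | 0-20% | 2.0 | 45-52% | 92-93% |
| 3.5 | 0-20% | 2.0 | 61-68% | 92-93% |
| 2.2 (SD 1.8) | 0-20% | 2.2 | 37-50% | 86-89% |
| 3.0 (SD 1.8) | 0-10% | 2.2 | 60-62% | 86-90% |
| 3.5 (SD 1.8) | 0-10% | 2.2 | 67-73% | 86-90% |
| 4.0 (SD 1.8) | 0-10% | 2.2 | 75-80% | 86-90% |

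In the first three rows:

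- 0-24% of patients had no computable value.
- The 5% of patients with the lowest non-zero baselines carried about 31-60% of the total sum of squares.
- Mean percent change exceeded the median by a factor of 192/53 = 3.6, 98/32 = 3.1 and 44/22 = 2.0.
- Percent change from an originating baseline (assumed mean about 7, no value below 2) had power of 80-86%.

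In the 2.2 row with 10% added zeros, about 11% of patients had no value, and the largest single value was typically about +2600%.

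**The case against.** The strongest reply is that little depends on this variable. It is exploratory. The itch score and absolute change are in the same row, and the next row gives 4-point improvement from the originating baseline. Section 6.1 says the substudy was not sized to detect differences. All of that stands, and it keeps the point minor.

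A second reply is that low IGA does not mean low itch. IGA scores erythema, papulation, oozing and lichenification, IGA 2 patients also enter, and a zero weekly mean needs every recorded day to be 0. This also stands. A reader might infer that substudy patients are all clear or nearly clear, or that a few near-zero baselines must dominate the result. The documents support neither; both depend on a distribution they do not give. At an assumed mean of 4.0 the power loss is modest.

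A third reply is that a constant 1-point effect favours absolute change by construction. That is fair, and it limits how literally the power gap should be read. It does not supply the missing rule for a zero denominator, and the formula's asymmetry at small baselines is arithmetic rather than assumption.

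Finally, Section 6.2.2 names itch change, not itch percent change. But percent change in itch is a continuous endpoint outside the EASI exception, and Appendix 2 lists it explicitly from Week 52.

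**Conclusion.** The point holds for Itch NRS percent change in the Period 2 substudy, and is likely to matter most in the Week 52 IGA 0/1 subset. As planned, the variable is undefined at a zero baseline, no rule covers that, and small baselines make it strongly right-skewed in a linear model. Under the assumptions above, power is about 37-80% against about 86-93% for absolute change. The direction is the same in every setting tried, but the size depends on the assumed Week 52 mean. Severity is minor.

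Three wider readings are not supported:

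- **EASI in general.** A reader might extend the point to EASI percent change in Table JAHN.6.5. Section 6.2.2 puts that on the originating-study baseline. EASI percent change from Week 52 is named only in Appendix 2, beside a Week 0 version; Section 6.11.3 names no outcomes.
- **SCORAD.** The row "Percent change from baseline in SCORAD score, Pruritus & Sleep Loss" is descriptive, in the long-term 4-mg population, which Section 6.2.1 defines regardless of substudy eligibility. No randomised comparison is affected.
- **Bias between arms.** A zero Week 52 value precedes rerandomisation, so excluding these patients need not favour either arm. The harm is a changed population and lost precision.

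**What to change.** - In Section 6.2.2 (Period 2) and Table JAHN.6.7, take Itch NRS percent change from the originating-study baseline, and from the JAHN baseline for addendum patients, as is already done for EASI. Alternatively, drop it.
- Keep absolute itch change from Week 52 with the Week 52 value as covariate.
- In Section 6.11.3, state that the Week 52-baseline sensitivity analyses exclude percent change.
- Reconcile Section 6.2.4 with Section 6.2.2. The former ties change to the originating-study baseline and leaves the percent-change denominator unnamed; the latter uses Week 52 for itch.
- State what happens to a zero baseline in any percent change that is kept. Addendum entry criteria set minimums for EASI, IGA and body surface area but none for itch, so the case is unlikely at entry but not excluded.
- If the Appendix 2 percent-change results from Week 52 (itch and EASI) are cited, give the number of patients without a computable value and rely on the Week 0 versions listed beside them.

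The cost is one exploratory display re-based or dropped, with no new data and no change to a primary or secondary analysis. Section 3 of the SAP says data up to Week 104 are locked, so this must be documented as a post-lock change with its reason.
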